10.4. Emergency Contact for Reporting Events and Device Deficiencies

Investigators should contact their responsible Medtronic study contact if they have any questions regarding reportable AEs or device deficiencies. Sponsor contact information (including name, title, address, and telephone number(s)) is subject to change and will be maintained in a document separate from the clinical investigation plan and provided to sites.

For reportable AEs or device deficiencies that require immediate reporting (see Table 7), initial reporting shall be done by completing the appropriate eCRF. If the eCRF is not available during the required reporting period, the reportable AE or device deficiency should be reported to Medtronic by alternate means, such as the responsible site manager. In due time, the reportable AE or device deficiency needs to be entered in the eCRF as well.

11. Data Review Committees

11.1. Clinical Event Committee

The Clinical Event Committee (CEC) is composed of independent cardiologists who are not participants in the study. The CEC is charged with the development of specific criteria used for the categorization of clinical events and clinical endpoints in the study. Criteria will be established for selected complications and clinical events. At the onset of the study, the CEC will establish explicit rules outlining the minimum amount of data required, and the algorithm followed in order to classify a clinical event. The CEC will meet regularly to review and adjudicate pre-defined clinical endpoint events. If needed, the adjudication committee will require collection of additional source documentation from the clinical centers. The procedures by which the CEC will operate will be documented in a separate CEC charter.

11.2. Data Safety and Monitoring Board

The Data Safety and Monitoring Board (DSMB) will evaluate safety data on an ongoing basis and advise Medtronic about the continuing safety of the study, to ensure the well-being of the current participants and those yet to be enrolled as well as the continuing validity and scientific merit of the study. The primary responsibility of the DSMB is to monitor the health, safety, and welfare of subjects. The DSMB will be composed of physicians from the fields of cardiology and interventional cardiology and at least one biostatistician with experience in analysis of clinical studies. The members of the DSMB will not be investigators in the study and will be independent of Medtronic.

Prior to the first DSMB review, guidelines for the identification and evaluation of significant safety findings and/or increased frequency of events that may impact the rights, safety or welfare of subjects will be established. All materials, discussions, and proceedings of the DSMB are completely confidential. The proceedings of each DSMB meeting will be recorded in

Medtronic Controlled Information

minutes. The DSMB Chairperson will be responsible for providing a written recommendation regarding study conduct (e.g., continue as planned, specify a modification, or termination) to Medtronic and the Study Principal Investigators. All final decisions, regarding study modifications rest with the Executive Committee and Sponsor. Details around the procedures of the DSMB are documented in a separate DSMB charter.

11.3. Executive Committee

The Executive Committee is composed of the study governance members including the study leadership and committee members. Their role is to provide overall supervision of the study, advise in study design, provide feedback on current practice and to assist in communications with clinical investigational sites. This committee will meet periodically by teleconference or in person to monitor the progress of the study, including subject enrollment, clinical site progress, and protocol compliance. The Executive committee will also be responsible for reviewing the final results and determining the methods of presentation and publication.

12. Statistical Design and Methods

The Onyx ONE Clear Study is a prospective, multi-center, single arm study for a commercially approved product. A total of 700 US subjects deemed at high risk for bleeding and/or medically unsuitable for more than one month DAPT treatment will be treated with the Resolute Onyx stent and studied for a one month DAPT treatment. Additionally, 100 subjects may be enrolled in Japan.

The primary objective is to evaluate the clinical safety of the Resolute Onyx stent as compared to the Performance Goal (PG) with use of one-month DAPT in subjects deemed at high risk for bleeding and/or medically unsuitable for more than one-month DAPT treatment.

12.1. Primary Endpoint

The primary endpoint in this trial is the composite of cardiac death and myocardial infarction at one year for a one-month clear population [timeframe: one month to one year].

12.1.1. Primary Hypothesis

The primary endpoint of the study will be compared to a PG of 9.7%. The study hypotheses are:

$$H_0: \pi \geq 9.7\%$$

$$H_A: \pi < 9.7\%$$

Where π denotes the binary rate of cardiac death and myocardial infarction at one year in a one-month clear population [timeframe: one month to one year]. This one-sided test will be carried out at the 0.025 significance level using the binomial exact test.

12.1.2. Hypothesis

Based on historical short DAPT studies with high-bleeding risk patient populations (LEADERS FREE, ZEUS, and SENIOR), the weighted average of cardiac death and myocardial infarction at one year was 9.6%. As disproportionately higher rates of STEMI, unstable angina, and multi-vessel disease were identified in the ZEUS study population which could have led to a higher rate of cardiac death, the ZEUS rate was revised. Similarly, the SENIOR rate contribution was derived from the published rates based on subjects with planned one-month DAPT use.

Approximately 3% of CD/MI events occurred in LEADERS FREE study at 30 days. To account for a “one-month clear” population, the weighted CD/MI rate at 12 months will be discounted by 3%, resulting in an average rate of 6.6%. In addition, to account for the 3% population that will also be removed from the denominator of the rates, the expected CD/MI rate between 30 days and one year is more accurately represented as 6.8%.

The performance goal (9.7%) incorporated a clinically acceptable margin of 2.9% to the expected rate.

In defining a “one-month clear” population, an attrition rate of 20% will be applied to account subjects who interrupted or discontinued DAPT (greater than 3 cumulative days) within the first one month of procedure, who were excluded due to events that would prohibit them from discontinuing DAPT beyond one month, who failed to transition from DAPT to SAPT one month after procedure, and who were lost to follow-up. Peri-procedural MIs will not exclude the patient from being considered as “one month clear”. For the secondary endpoints like TLF, all available biomarkers (including peri-procedural) will be forwarded to the CEC to be used towards the adjudication of events.

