One-month clear	
Subjects who are event-free of any the following within one month after stenting: myocardial infarction (MI), repeat coronary revascularization, stroke, stent thrombosis (ARC definite/probable), and death. Subject must be adherent to DAPT for the total 1-month period, where adherence means without interruption of aspirin and/or P2Y12 inhibitor for >3 days. Subjects discontinue either aspirin or P2Y12 inhibitor after one month and continue on single antiplatelet therapy (SAPT).*
 
*Please refer to sections in this protocol on planned staging procedures and anti-coagulant use for extended definitions concerning 1-month DAPT use.

Oral anticoagulant (OAC)	Type of oral medication used to prevent or reduce coagulation of blood. Includes vitamin K antagonists (e.g. warfarin) and novel anticoagulants (NOACs)/ directly acting oral anticoagulants (DOACs) (e.g. apixaban, rivaroxaban, dabigatran, edoxaban)
Percent diameter stenosis (%DS)	The value calculated as 100 x (RVD – MLD)/RVD using the mean values from two orthogonal views (when possible). Percent diameter stenosis is visually estimated during angiography by the Investigator.

Acronyms / Terms	Definition
Percutaneous coronary intervention (PCI)	All interventional cardiology methods for treatment of coronary artery disease.
Perforation	Perforations will be classified as follows: Angiographic perforation: perforation detected by the clinical site or the core laboratory at any point during the procedure. Clinical perforation: perforation requiring additional treatment (including efforts to seal the perforation or pericardial drainage), or resulting in significant pericardial effusion, acute closure, myocardial infarction, or death. Pericardial hemorrhage/tamponade: perforation resulting in cardiac tamponade.
POBA	Plain old balloon angioplasty
Procedure success	Attainment of <30% residual stenosis by QCA (or <20% by visual assessment) AND TIMI flow 3 after the procedure, using any percutaneous method without the occurrence of MACE during the hospital stay.
PTCA	Percutaneous transluminal coronary angioplasty
QCA	Quantitative coronary angiography
QWMI	Q wave myocardial infarction
RDC	Oracle Clinical Remote Data Capture
Restenotic lesion	A lesion in a vessel segment that has undergone prior percutaneous treatment with or without a stent placement.

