8.6. Medication Adherence

Patient adherence to the one-month DAPT regimen is highly important for this study. The investigator and team should take extra steps to ensure this is communicated with the patient. To be deemed one-month clear for DAPT discontinuation at 1-month, subjects must not interrupt aspirin and/or P2Y12 inhibitor for longer than 3 days during the first month after the index PCI or last staged PCI procedure. Subjects must also continue on single antiplatelet therapy (SAPT) after one month of DAPT through the end of the study. Subjects will be provided a medication reminder card and also instructed to inform the investigator and team on any changes in medication including medication stop date, reason for stopping medication, medication restart date, and medication dosage. Dual antiplatelet therapy compliance will be assessed in the clinic at the 1-month visit as well as in follow-up contacts and will be recorded in the eCRF.

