5.1. Sample Size for Primary Objective

Based on historical short DAPT studies with high-bleeding risk patient populations (LEADERS FREE, ZEUS, and SENIOR)^{1,2,3,4,5} the weighted average of cardiac death and myocardial infarction at one year was 9.6%. As disproportionately higher rates of STEMI, unstable angina, and multi-vessel disease were identified in the ZEUS study population which could have led to a higher rate of cardiac death, the ZEUS rate was revised. Similarly, the SENIOR rate contribution was derived from the published rates based on subjects with planned one-month DAPT use.

Approximately 3% of CD/MI events occurred in LEADERS FREE study at 30 days. To account for a “one-month clear” population, the weighted CD/MI rate at 12 months will be discounted by 3%, resulting in an average rate of 6.6%. In addition, to account for the 3% population that will also be removed from the denominator of the rates, the expected CD/MI rate between 30 days and one year is more accurately represented as 6.8%.

The performance goal (9.7%) incorporated a clinically acceptable margin of 2.9% to the expected rate.

In defining a “one-month clear” population, an attrition rate of 20% will be applied to account subjects who interrupted or discontinued DAPT (greater than 3 cumulative days) within the first one month of procedure, who were excluded due to events that would prohibit them from discontinuing DAPT beyond one month, who failed to transition from DAPT to single antiplatelet therapy (SAPT) one month after procedure, and who were lost to follow-up. Peri-procedural MIs will not exclude the patient from being considered as “one month clear”. For the secondary endpoints like TLF, all available biomarkers (including peri-procedural) will be forwarded to the CEC to be used towards the adjudication of events.

Assuming a one-sided alpha level of 0.025 and a true event rate of 6.8%, an effective sample size of 1360 subjects will yield a greater than 97% power to reject the null hypothesis. Assuming a 20% attrition rate, a total sample size of 1700 subjects will be needed.

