6.6. Analysis of Subgroups

Subgroup analyses of the primary and secondary endpoints (AT set, AT set for one-month clear population) include the following patient characteristics.

- Acute Coronary Syndrome (ACS) vs. no ACS
Acute coronary syndrome is NSTEMI or STEMI, or unstable angina at baseline
- Diabetes vs. no diabetes
- Age (≤ 75 vs. > 75 years)
- Sex (female vs. male)
- Multi-vessel vs. Single vessel treatment
- Multi-lesion vs. Single lesion treatment
- Overlapping stent vs. none
- Off-label (Complex) vs. on-label (Simple)

For the purposes of stratification, subjects are considered “complex” if they have total occlusion or are off-label because of any of these conditions: bifurcation, saphenous vein graft (SVG), target lesion in-stent restenosis (ISR), Acute MI (≤ 72 hrs), left ventricular ejection fraction (LVEF) $< 30\%$, unprotected left main (LM), more than two vessels stented, renal insufficiency or failure (creatinine ≥ 140 $\mu\text{mol/L}$), lesion length

Revision 4.0

> 35 mm, more than one lesion per vessel, or pre-procedure thrombus. “Simple” subjects are all the subjects excluding “complex” subjects. “Simple” subjects are also on-label subjects except those have total occlusion.

- US vs. Japan (p-value from comparing US subjects to Japan subjects will be calculated)
- With staged procedure vs. without staged procedure
- OAC vs no OAC planned to continue after PCI
- Renal failure (creatinine clearance < 40 ml/min) vs. no renal failure
- Minimum stent diameter ≤ 2.5 mm vs. > 2.5 mm
- With vs without anemia or hospital admission for bleeding < 12 months
- With vs without planned major surgery during the next 12 months
- Total stent length ≤ 30 mm vs. > 30 mm
- Femoral vs. non-femoral final vascular access site
- Enrolled by age criteria only vs. not enrolled by age criteria only
- Bifurcation vs. none
- Subjects switched from DAPT to SAPT between 27 days and 35 days post procedure, to be referred to as a “medication adherent subgroup”
- Number of HBR criteria
- SAPT type after one month: aspirin vs. P2Y12 inhibitor. This only applies to one-month clear population and who actually transitioned to SAPT from DAPT.

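### The visible text conflicts on whether one-month clear membership requires the switch to SAPT; if it does, a subject with an MI just before the switch can leave the primary set together with the event

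*Protocol*

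**What the plan says.** The primary endpoint is cardiac death or MI from one month to one year in the one-month clear population, compared with a performance goal of 9.7%. The test is described in protocol 12.1.1: "This one-sided test will be carried out at the 0.025 significance level using the binomial exact test".

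Some passages tie membership to the switch:
- Protocol 12.1.2 introduces a 20% attrition allowance in defining the one-month clear population. Besides first-month DAPT interruption and excluding events, it lists subjects "who failed to transition from DAPT to SAPT one month after procedure, and who were lost to follow-up".
- SAP 5.1 repeats the list, including those "who failed to transition from DAPT to single antiplatelet therapy (SAPT) one month after procedure".
- The glossary entry for one-month clear, after its event and adherence conditions, ends with "Subjects discontinue either aspirin or P2Y12 inhibitor after one month and continue on single antiplatelet therapy (SAPT". Protocol 5.2 closes its definition in the same way.

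Other passages point away from that:
- SAP 6.6 restricts the SAPT-type subgroup: "This only applies to one-month clear population and who actually transitioned to SAPT from DAPT". That restriction would be redundant if every one-month clear subject had switched.
- SAP 6.6 also makes switching on days 27 to 35 a subgroup (the medication adherent subgroup), not an entry condition.
- The visible event-free rule in SAP 6.1 lists clinical events only. The three membership bullets next to it are redacted.

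**The concern.** Primary events start to count at one month, so membership should be settled by what is known at that landmark. Whether a subject switches can be decided after it: the visit window is 30 ± 5 days, and even the medication adherent subgroup may switch up to day 35. The endpoint itself can change that decision. A subject with an MI on day 32 who has not yet switched and is kept on DAPT can be classed as having failed to transition. That subject then leaves the primary set, and a primary event leaves too.

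Removal by this route takes out event subjects only, so the bias runs toward meeting the goal. Nothing in the primary analysis recovers the event. The numerator in SAP 6.4.2 counts only one-month clear subjects, and the missing-data sensitivity analyses in SAP 6.4.5 cover only one-month clear AT subjects. This is the study's only hypothesis test. It is single-arm against a fixed goal, and the report is intended to support market approval.

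**Working it through.** **1. The plan's own figures.** Inputs: goal 9.7%, one-sided 0.025, exact binomial (protocol 12.1.1); true rate 6.8%, 1360 evaluable, 20% attrition (protocol 12.1.3).
- Critical count: the largest c with P(X ≤ c | 1360, 0.097) ≤ 0.025 is c = 110, with attained level 0.0227.
- Power: P(X ≤ 110 | 1360, 0.068) = 0.971, which agrees with the stated figure of more than 97%.
- Total: 1360/0.80 = 1700, as stated.

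**2. How many events could be caught between the landmark and the switch.** The documents give no figure, so this is an assumed range. Take 1360 subjects at the landmark, a true rate of 9.7%, and events spread evenly over days 31 to 365 (335 days).
- Expected events: 1360 × 0.097 = 131.9.
- Events on days 31–35: 131.9 × 5/335 = 1.97. This is the upper end: nobody has switched by day 35, and deaths are removed as well.
- MI only: the one-year BioFreedom rates from LEADERS FREE in protocol 3.1 are MI 6.1% and cardiac death 4.2%, so the MI share is about 6.1/(6.1 + 4.2) = 0.59, and 1.97 × 0.59 = 1.17. The share is rough. Those rates include the first month, and the components overlap (6.1 + 4.2 = 10.3, above the 9.4% composite that also includes stent thrombosis).
- MI only, with half of the subjects already switched (assumed): 1.17/2 = 0.58.

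**3. Effect on the test at a true 9.7%.** If a fraction f of event subjects is removed from numerator and denominator, the observed rate is p(1 − f)/(1 − pf) and n becomes 1360(1 − pf). The critical count stays at 110 in each row.

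| Event subjects removed | f | Rate | n | False success |
|---|---|---|---|---|
| 0 | 0 | 9.70% | 1360 | 2.3% |
| 0.58 | 0.0044 | 9.66% | 1359 | 2.6% |
| 1.17 | 0.0088 | 9.62% | 1359 | 2.9% |
| 1.97 | 0.015 | 9.57% | 1358 | 3.4% |

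Removing exactly two event subjects gives P(X ≤ 112 | 1360, 0.097) = 3.5%.

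**4. Effect of fixing membership at the landmark.** With no event-dependent removal, false success is 2.3%. Power at 6.8% is 97.1% with 1360 subjects, and would be 99.0% (critical count 140) if all 1700 stayed in. Keeping non-switchers therefore costs no power.

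**The case against.** The strongest reply is that the list in protocol 12.1.2 and SAP 5.1 is a sample-size allowance, not a membership rule. It also contains loss to follow-up, which SAP 6.4.2 and 6.4.5 treat as missing data among subjects who are already members. The operative definition is in SAP 6.1, where redaction hides it, and redaction is not a fault. SAP 6.6 suggests that the switch is not required. All of this stands, and it is why the documents cannot be said to build the primary set this way. It does not remove the conflict: the list is introduced as part of defining the population, and two protocol definitions end with the switch.

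It can also be said that 1360 is already net of non-switchers. That affects the exact base for the calculation, but not the direction or the order of size.

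A reader might infer something stronger: that a subject who has an MI months later and returns to DAPT also drops out, with a large effect on the error rate. Protocol 8.6 does say "Subjects must also continue on single antiplatelet therapy (SAPT) after one month of DAPT through the end of the study", but the sentence there that sets the condition for being one-month clear covers first-month interruption only, and this one follows as a separate conduct requirement. The closing clause in the glossary and 5.2 about continuing on SAPT can be read as describing the regimen. SAP 6.4.2 counts every cardiac death or MI of a one-month clear subject to day 365, whatever the later therapy. The documents do not support that reading.

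There is partial mitigation. Cardiac death/MI on the full AT set is a planned secondary analysis (SAP 6.5.1), but the AT set's time zero is the index procedure (SAP 6.1), so it does not isolate the period after one month. The 30-day landmark analysis in SAP 6.7 does, but it is for publication only.

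**Conclusion.** The point holds as a conflict in the visible text with a known direction of bias. The protocol wording allows non-switchers to be removed, and SAP 6.6 implies that they stay. Under the protocol wording, an MI between day 30 and the switch can disappear from the primary analysis.

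The size is probably small: false success of about 2.6–3.5% against an attained 2.3%, the low end barely above the nominal 2.5%. This rests on 1360 subjects at the landmark, a true rate of 9.7%, a uniform hazard, a switch by about day 35, and 0.5 to 2 event subjects removed. A higher hazard soon after the landmark, or later switching, would raise it. The correction is worth making because it is cheap and concerns who enters the only confirmatory test. The documents do not show that the primary analysis is invalid.

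**What to change.** - **Membership.** In the protocol glossary, 5.2 and 12.1.2, and in SAP 5.1 and 6.1, state that one-month clear status uses only information up to the landmark: first-month DAPT adherence and event freedom, extended to one month after the last planned staged procedure as in protocol 8.8. State that failure to transition to SAPT does not remove a subject from the AT one-month clear set.
- **Reporting.** Give the number of one-month clear subjects who did not transition. Keep the medication adherent subgroup in SAP 6.6 for the on-regimen picture.
- **Sensitivity analysis.** Move the 30-day landmark analysis of cardiac death/MI on the AT set from SAP 6.7 into the study report. It keeps subjects with non-fatal events before day 30, so it answers a wider question and should be read as supportive, not as a second test of the goal.

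The cost is wording in both documents, one population flag and one extra table. The drawback is that some subjects who stayed on DAPT remain in the primary set, which is why their number should be shown. No change to treatment is implied.

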12.1.3. Sample Size Calculation and Methods

Assuming a one-sided alpha level of 0.025 and a true event rate of 6.8%, an effective sample size of 1360 subjects will yield a greater than 97% power to reject the null hypothesis. Assuming a 20% attrition rate, a total sample size of 1700 subjects will be needed.

The outcomes from 700 US subjects enrolled in this study will be combined with those of 1000 subjects from the Resolute Onyx arm of the Onyx ONE Study to form the total sample size of 1700. In addition, subjects enrolled in Japan who have completed their one-year follow-up at the time when the 700 US subjects have completed their one year follow up will also be included in the primary analysis.

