6.1. Analysis Populations

Per the CIP, subjects will be considered enrolled into the trial after the following criteria have been met:

1. The signed and dated informed consent has been obtained
2. The patient and target vessel(s)/lesion(s) have met all of the inclusion and none of the exclusion criteria

Revision 4.0

3. The study stent is introduced into the guide catheter

Intent-to-Treat (ITT): All enrolled subjects. Time zero begins at the date of the index procedure.

As Treated (AT): All ITT subjects who received the Resolute ONYX stent only. Time zero begins at the date of the index procedure.

One-month Clear: All subjects who meet all of the following criteria:

- [REDACTED]
- [REDACTED]
- [REDACTED]

[REDACTED]

[REDACTED]

Event-free is defined as that a subject must not have myocardial infarction (MI) (excluding peri-procedural MIs), repeat coronary revascularization, stroke, stent thrombosis (ARC definite/probable), and death. [REDACTED]

[REDACTED]

As Treated and Intent-to-Treat for one-month clear are:

- As Treated Set for One-month Clear: All AT subjects who are in the one-month clear population. This is the primary cohort for the primary endpoint analysis.
- Intent-to-Treat Set for One-month Clear: All ITT subjects who are in the one-month clear population.

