6.5.1. Data Collection and Analysis Methods

The data on the CEC adjudication form will be used in the analysis. For secondary endpoints, event rates/success rates, and 95% two-sided confidence interval will be provided. The time-sensitive nature of any response variable will be displayed by using a Kaplan-Meier plot.

The primary analysis for secondary endpoints at follow-up time points (2, 6 months, 1 and 2 years) will be performed for AT one-month clear population, except that the acute success. The secondary analysis for secondary endpoints (except acute success) at all follow-up time points (1, 2, 6 months, 1 and 2 years) will be performed based on the AT set.

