6.7. Analysis for Publications for Extension of Onyx One Global RCT Study

This section describes the planned analyses for publication purpose only. Baseline demographic and clinical data from the pooled Resolute Onyx subjects will be compared to the data from the BioFreedom arm of Onyx One study for ITT, AT, and AT one-month clear sets. The cumulative analysis (from one month to 365 days post procedure) will be performed for the AT one-month clear population and the landmark analysis will be performed for ITT and AT sets on all clinical endpoints and for all subgroups defined in Section 6.6 except the US vs Japan subgroup, Medication Adherent subgroup, and SAPT type after one-month subgroup. The analysis populations for the cumulative and landmark analyses are specified in Tables 1 to 2.

Landmark analyses at 30 days for all clinical endpoints will be performed for the AT and ITT set, and will be compared to the corresponding populations in the BioFreedom arm of Onyx One Global RCT study. The Kaplan Meier method will be used to calculate event rates for events that occur between 31- and 365-days post index procedure. Subjects who died or withdrew before 30 days will be excluded from this analysis. Subjects who experienced non-terminal events (e.g., MI) before 30 days will be included from this analysis. The cumulative incidence function in the presence of a competing risk will be estimated, and comparisons between Onyx and BioFreedom arms will be made using Gray’s test.

Table 1. Analysis Populations for Pooled Cumulative Analysis

Cumulative Analysis	Planned Analysis	Analysis Population for Cumulative Analysis
All clinical endpoints, from one month to one year	Principal effective and safety table	AT one month clear

Revision 4.0

Subgroup analysis from one month to one year	Principal effective and safety table	AT one month clear
--	--------------------------------------	--------------------

Table 2. Analysis Populations for Pooled Landmark Analysis

Landmark Analysis	Planned Analysis	Analysis Population for Landmark Analysis
All clinical endpoints, from 30 days to one year	Principal effective and safety table	ITT/AT
Subgroup analysis from 30 days to one year	Principal effective and safety table	ITT/AT

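### No start day is given for counting events in the one-month clear set, so peri-procedural MIs can enter the secondary composites and, on the text of SAP 6.4.2, the primary endpoint as well

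*Protocol*

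**What the plan says.** **Clear status.** Protocol 12.1.2 and SAP 5.1 let a subject with a peri-procedural MI remain one-month clear. SAP 6.1 builds this into the population: "Event-free is defined as that a subject must not have myocardial infarction (MI) (excluding peri-procedural MIs), repeat coronary revascularization, stroke, stent thrombosis" (the list ends with death). The protocol glossary and section 5.2 list MI among the disqualifying events without this exception.

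**Adjudication.** Protocol 12.1.2, repeated in SAP 5.1, continues: "For the secondary endpoints like TLF, all available biomarkers (including peri-procedural) will be forwarded to the CEC to be used towards the adjudication of events".

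**Secondary endpoints.** SAP 6.5.1 says that their primary analysis at 2 and 6 months and 1 and 2 years "will be performed for AT one-month clear population, except that the acute success". Neither SAP 6.5 nor 6.5.1 says from which day events count. Protocol 12.2 sets time zero of the primary analysis population at the index procedure, and SAP 6.1 does the same for the AT set.

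**Primary endpoint.** Its time frame is one month to one year (Protocol 12.1, SAP 3.1 and 6.4). The operational numerator in SAP 6.4.2, however, takes clear subjects with cardiac death or MI up to day 365 and sets no earliest day.

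**Publications.** Only SAP 6.7 gives an explicit one-month start for all clinical endpoints in this set: "The cumulative analysis (from one month to 365 days post procedure) will be performed for the AT one-month clear population". That section is limited to publications.

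**The concern.** First-month cardiac death, non-procedural MI and repeat revascularization remove both the event and the subject from the clear set. Peri-procedural MI is the only component of CD/MI, MACE, TLF and TVF that can occur in the first month and leave the subject in. If counting runs from time zero, a one-year rate in this set is procedural MIs (target-vessel MIs for TLF and TVF) plus events after one month. It omits the other early events, so it is not a 0-12 month rate. It includes the procedure, so it is not a 1-12 month rate and does not describe risk after DAPT is stopped.

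Two things are at stake. The study report and the publication could give different TLF, TVF or MACE rates for the same subjects. And if the SAP 6.4.2 numerator were programmed as worded, the primary test would count events that the 6.8% assumption leaves out.

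**Working it through.** **1. Reproduce the plan's figure.** Protocol 12.1.1: "The primary endpoint of the study will be compared to a PG of 9.7" percent, and "This one-sided test will be carried out at the 0.025 significance level using the binomial exact test". Protocol 12.1.3: "a true event rate of 6.8%, an effective sample size of 1360 subjects will yield a greater than 97% power"; "Assuming a 20% attrition rate, a total sample size of 1700 subjects will be needed".

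- Expected rate: 9.6 − 3.0 = 6.6; 6.6/0.97 = 6.80%. Goal: 6.8 + 2.9 = 9.7%.
- Sample size: 1360/(1 − 0.20) = 1700.
- Exact test with n = 1360 and p0 = 0.097: the largest c with P(X ≤ c) ≤ 0.025 is c = 110 (8.09%), with actual alpha 0.0227. The exact two-sided 95% upper limit is 9.67% at 110 events and 9.75% at 111, so the confidence-limit rule in SAP 6.4.3 gives the same cut-off.
- Power at 6.8%: P(X ≤ 110) = 0.9714. The stated figure of more than 97% is reproduced.

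**2. What the 6.8% contains.** The 3 points by 30 days come out of both numerator and denominator. The assumption therefore describes events after one month only, with no procedural MI.

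**3. Rate if peri-procedural MIs count.** The documents give no peri-procedural MI rate. Let x be the assumed proportion of clear subjects with one, independent of later events. One-year CD/MI is then 0.068 + x(1 − 0.068). The last column is P(X ≤ 110) at that rate with n = 1360, and applies only if these MIs enter the primary numerator.

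| x (assumed) | One-year CD/MI | Subjects of 1360 | Power if counted in the primary |
|---|---|---|---|
| 0 | 6.8% | 92 | 97.1% |
| 0.5% | 7.3% | 99 | 88.8% |
| 1% | 7.7% | 105 | 71.0% |
| 2% | 8.7% | 118 | 24.2% |
| 3% | 9.6% | 130 | about 3% |

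The last row is an extreme. It corresponds roughly to all of the plan's 3% first-month CD/MI being peri-procedural.

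**4. Rate if counting starts at one month.** Subjects with a peri-procedural MI stay in the denominator but add no early event. The expected rate is about 6.6/(97 + 100x): 6.77% at x = 0.5% and 6.60% at x = 3%. It does not exceed the planned 6.8%, so the design power is kept.

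**5. A sign that the text is unsettled.** SAP 6.4.2 also asks for a one-month Kaplan-Meier rate of the primary composite. In the clear set that rate is essentially zero by construction unless peri-procedural MIs count.

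**The case against.** The best defence is that counting from day 0 is nowhere stated as a rule. Sending biomarkers to the CEC describes what the adjudicators see, not the set or window in which an MI is counted. Peri-procedural MIs already have a place in the AT-set rates and in procedure success. Time zero at index does not by itself mean counting from index, since the primary analysis population has that time zero and a one-month time frame. SAP 6.5 drops the 1-month time point for the clear set, which hints at a later start, and SAP 6.7 uses one. Parts of SAP 6.1 are redacted.

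Most of this stands, and it makes the point one of silence rather than of a wrong rule. It does not remove the gap. The redactions fall in the population definition, whereas the counting text for secondary endpoints in SAP 6.5 and 6.5.1 is visible and names no start.

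A reader might infer more than the documents support:

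- *That the report must show two conflicting one-year CD/MI rates.* This needs the primary to start at one month and the secondary at day 0. On the literal SAP 6.4.2 numerator the two agree, but the primary then departs from its own time frame.
- *That peri-procedural MI is the only first-month event of any kind that leaves a subject clear.* Bleeding is not on the visible list either. The statement holds only for components of the four composites.
- *That a secondary rate near 9.7% would be a failure.* Secondary endpoints get rates and confidence intervals, with no test against the goal.
- *That the rates would depend on whether sites draw markers at all.* Protocol 8.1.1 requires at least one post-procedural CK/CK-MB or troponin measurement.

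**Conclusion.** The concern holds as a missing start day with two consequences. In the AT one-month clear set, the study-report CD/MI, MACE, TLF and TVF rates can mix procedural MIs with events after one month. The same is true of the primary endpoint if the SAP 6.4.2 numerator is taken as worded. Such rates match neither the 6.8% assumption nor the one-month start in SAP 6.7.

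The stated power is correct for the intended window. The possible shift, from 6.8% to between 7.3% and 9.6%, and the loss of power to between about 89% and 3%, rest on assumed peri-procedural MI rates of 0.5% to 3%, independence from later events, and 1360 evaluable subjects. They show how sensitive the result is to the reading and do not predict it. The issue is worth settling before the analysis is programmed, because the choice of reading changes reported results and could change the primary conclusion.

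**What to change.** - **SAP 6.4.2:** add the lower bound to the numerator, so that it takes cardiac death or MI after one month, or after one month from the last planned staged procedure, through day 365. Protocol 8.8 already extends the clear definition in this way.
- **SAP 6.5 and 6.5.1:** state that CD/MI, MACE, TLF, TVF and their MI components in the AT one-month clear set are counted from that same start to each later time point. Pointing only to the primary endpoint's start is not enough until SAP 6.4.2 contains one.
- **Protocol 12.1.2 and SAP 5.1:** state that peri-procedural MIs count only in AT-set rates measured from the index procedure and in procedure success.
- **Protocol glossary and section 5.2:** add the peri-procedural MI exception to the one-month clear definition, to agree with Protocol 12.1.2 and SAP 6.1.

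The cost is a few sentences and one date filter in the tables, with no new data and no change to sample size. Rates from the index procedure remain available in the AT-set analysis that is already planned.
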